The Role of Biodentine in Class V Dental Lesions on Oral Health Related Quality of Life

NCT03304184

Date last modified: July 13, 2018

SPECIFIC AIMS

More than 45 million adults suffer from overly sensitive teeth in the United States [1] which affects women more than men [2]. Tooth sensitivity leads sufferers to avoid many of their favorite foods because the temperature of the food can lead to a sharp intense pain. Even cold atmospheric air can trigger extreme pain [3]. Tooth sensitivity can be chronic causing a disruption in daily activities of the affected individuals, thereby seriously impacting their oral health related quality of life [4].

Tooth sensitivity occurs when the dentin and dentin tubules that contain fluid along with nerve endings are exposed due to the removal of a protective layer surrounding dentin called cementum. This process of cementum removal is frequently associated with gingival recession caused by aggressive tooth brushing. Improper tooth brushing techniques can cause the toothbrush bristles to act like a saw at the gumline. The saw-like action creates a V shaped lesion thereby exposing dentin [5] (Fig. 1), which is frequently associated with tooth sensitivity [6]. Once the dentin is exposed, the fluid inside the dentin tubules can move by changes in osmotic pressure (Fig. 1C) [7]. This movement leads to perceived pain via activation of nociceptors. For the purposes of this study, we will be referring to tooth sensitivity as tooth pain because of the activation of nociceptors within the pulp [8]. Commonly, patients that suffer from extreme tooth pain associated with V shaped lesions are treated with non-restorative and restorative treatments that include the use of over-the-counter fluoride, prescription fluoride, sensitivity reducing medicaments, toothpastes containing potassium nitrates and restorations with dental materials that cover the affected area [9, 10].

Despite numerous ways to treat tooth pain associated with V shaped lesions, most of them are unsuccessful at reducing the discomfort permanently [11].

For very symptomatic V shaped lesions, a resin-modified glass ionomer restoration may be the preferred treatment [9, 10, 12]. This material covers and seals the dentin tubules, providing a protective layer where the cementum has worn away. However, resin-modified glass ionomer restorations do not always reduce or diminish the tooth pain because the chemical makeup of resin-modified glass ionomers themselves may trigger tooth irritation through an inflammatory response in the pulp [13]. Therefore, it is important to evaluate new dental materials that may be more effective in treating the pain associated with tooth sensitivity with fewer negative sequelae. A new biocompatible and bioactive material (Biodentine™) is available. Biodentine™ has a wide range of clinical applications because of its similarity to the dentin and its mechanisms of dentin adherence. Furthermore, Biodentine™ has been successfully used as a safe dentin substitute in clinical studies[14]. However, the effect of Biodentine™ to reduce tooth pain in V shaped lesions is unknown.

We propose to investigate the effect of Biodentine™ as a restorative dental material on V shaped lesions with a randomized single blind controlled study. Specifically, we will investigate how Biodentine™ treatment affects oral health related quality of life. Because Biodentine™ is a biocompatible and a bioactive material, which is considered a dentin substitute material, we hypothesize that Biodentine™ is a more effective way of treating tooth pain associated with V shaped lesions compared to traditional resin-modified glass ionomer restorations. To evaluate the effects of Biodentine™ as a dental restorative material, we will compare the treatment with Biodentine™ to the resin modified glass ionomer, which is a dental material widely used to restore V shaped lesions. In addition, we will evaluate the impact on oral health via patient self-reporting of pain and daily activities with an oral health related quality of life questionnaire before and after treatment at multiple time points.

Specific Aims (SA):

SA1: Investigate whether Biodentine™ is more effective compared to resin-modified glass ionomer in reducing tooth pain in V shaped lesions

SA 2: Investigate whether Biodentine™ is more effective compared to glass resin-modified ionomer in improving general oral health-related quality of life in patients with V shaped lesions.

[figure not shown]

Figure 1: Tooth diagram. Enamel is in white and dentin is in pink. **A)** Shows the exposed region of dentin on a tooth where nerve endings can be exposed; **B)** is the recessed gingiva created by excess tooth brushing; **C)** Dentin tubules containing the nerves.

In the mission of the PORT grant, these data will help identify a new material to effectively treat patients suffering from tooth pain in V shaped lesions, which may lead to improve oral health related quality of life.

RESEARCH STRATEGY

Significance

Pain associated with tooth sensitivity is highly prevalent among the US adult population [1]. Considering the adult population, women and men aged 30-40 years old are both affected by tooth sensitivity and women tend to show a slightly higher prevalence than men. In addition, as the population ages, tooth sensitivity is frequently caused by V shaped lesions and by intensified brushing activity after gum disease [2, 15]. Despite the large number of affected individuals with tooth sensitivity associated pain [16, 17], the impact of tooth pain from V shaped lesions in the oral health related quality of life (OHRQL) is still unknown. Surprisingly, no evidence-based guidelines to treat tooth pain from V shaped lesions exist and the condition is merely managed with two basic approaches without any concern for OHRQL outcomes [18]. The first approach uses chemical agents to temporarily reduce tooth pain by plugging dentin tubules[19]. The second approach uses the placement of a dental restoration. However, both approaches are not always effective and require periodic reevaluations. In addition, the majority of studies evaluating tooth pain related to V shaped lesions did not assess the psychological component of pain from these lesions [20, 21]. There is a current gap in knowledge characterizing the patient OHRQL in individuals suffering from pain in V shaped lesions before and after treatment. Consequently, the assessment of OHRQL in affected patients may help identify better treatment strategies. Furthermore, it is difficult to estimate the impact of tooth pain in the patients' quality of life because many patients fail to inform their clinician of sensitivity issues they experience [22]. Therefore, this study expects to contribute to the knowledge of the impact of tooth pain associated with V shaped lesions in OHRQL.

Given the restraints of the current approaches to treat tooth pain on OHRQL, our study proposes to investigate the impact of tooth pain associated with V shaped lesions with a widely used OHRQL questionnaire, the Oral Health Impact Profile-49 (OHIP-49). The OHIP-49 questionnaire has been extensively validated to evaluate the impacts of oral health in people's ability to function psycho-socially in regards to dental health and perceived health prior to treatment and at multiple time points after treatment [23]. Lastly, in summary, our study will contribute to the knowledge of the treatment of V shaped sensitive lesions and will assess the impact of tooth pain in the quality of life before and after treatment on V shaped lesions.

Innovation

Despite the millions of patients suffering from tooth sensitivity, a treatment that effectively eliminates tooth pain associated with V shaped lesions near the gumline does not exist. More importantly, dental materials in the market are highly sensitive to placement under damp conditions. Placing restorations near the gum tissue, which is the primary location for the V shaped lesions, poses a challenge even for a talented clinician. The main reason for failure of dental restorations is contamination from saliva, which results in microleakage at the margins of the restoration. This leakage can cause fluctuations in the fluid in the dentin tubules and leads to pain, even when the restoration is present. Moreover, some of the materials placed in these lesions can cause an increased inflammatory response because they are placed on the dentin which contains tubules that lead directly to the pulp (Fig. 1) and cause more irritation in the pulp and perceived pain [24].

Therefore, this study is innovative because it proposes to evaluate a new bioactive and biocompatible dental material as it relates to diminishing tooth pain. More specifically, our study includes four important innovative aspects: 1) Biodentine™ is biocompatible and bioactive, which may suppress inflammatory pulp responses and promote better marginal seal [25-28]; 2) Biodentine™ relies on the presence of biofluids to form hydroxyapatite crystals [24] [25]; 3) Biodentine™ derived hydroxyapatite crystals (naturally present in the tooth structure) may result in more long-lasting effects on tooth pain [29]. More importantly, 4) we propose to evaluate the impact of V shaped lesions associated tooth pain in our patients' quality of life before and after the proposed alternative treatments.

The lack of guidelines to treat tooth pain associated with V shaped lesions is an important area of study [30, 31]. In addition, despite the many treatments used by clinicians to treat pain in V shaped lesions there is little evidence of their effectiveness [27]. The results of our study will provide evidence to fulfill an enormous lack of

knowledge in the dentistry, which will ultimately help clinicians make appropriate treatment decisions to treat tooth pain associated with V shaped lesions. More importantly our study may contribute to the knowledge of the impact of pain associated with V shaped lesions in the patients' overall quality of life.

Approach

Study Design

The proposed study is a two-year single blind study with blinded assessors to evaluate participant responses about chronic pain from V shaped tooth lesions. The participants will be recruited from the University of Michigan School of Dentistry and will be treated with a traditional dental material and with a new dental material. Participants will fill out screening questions to determine eligibility. Once enrolled they will either receive the traditional treatment for a sensitive V shaped lesion or will be treated with the new material Biodentine™. Participants will be evaluated prior to treatment and post treatment at 1 week, 2 weeks, and 3 months to determine the effects of the two different treatment modalities on OHRQL.

Participants

Men and women from the ages of 18-64 years old will be recruited from the University of Michigan School of Dentistry because of their prevalence of pain associated with V shaped lesions. Additionally, the study will be capped at the age of 64 because of the pathologic changes occurring within the pulp due to the natural aging of a tooth by the addition of secondary dentin within the pulp. This can lead to inconclusive pulp testing results in older individuals [15, 32]. Participants enrolled will be limited to those whose chief complaint is chronic tooth pain associated with V shaped lesions and that the lesion is non-carious and located near or at the gumline (Table 1). Participants will be on limited medications to avoid the effects of polypharmacy, more specifically the effects on reducing saliva flow which enhances the risk for caries development. The affected teeth will have the pulp vitality evaluated with an electronic pulp tester, which is a device that can assess the vitality of the tooth with a quantifiable number. Pulp test readings must be below 40 to be considered for the study. Participants will also be asked what their average pain is when the tooth pain is triggered and must register over a 6 point in the self-report brief pain inventory index for each question asked to the patient. All participants will have tooth-associated pain for more than 2 months to meet inclusion criteria. Both of these short assessments will be measured on a 1-10 Likert scale. See Table 1 for inclusions and exclusions. If a participant has two or more teeth in the associated quadrant that have associated chronic pain, we will fill up to two sites that are innervated by the same nerve. Participants must be fluent in English in order to fill out the surveys and have at home access to a computer or the ability to come to the school of dentistry to fill out the survey on a supplied iPad®.

Participants will be excluded from the study if their dental health requires treatment from multiple disciplines of dentistry, including endodontics (root canals) and periodontics (active periodontal disease). Participants with extensive systemic health problems will also be excluded. Participants with low saliva flow (Xerostomia) will be excluded – typically if the participant is on more than 2 medications that reduce salivary flow. The baseline

Table 1. Study Inclusion and Exclusion Criteria

Inclusion Criteria

 • Males and females age 18-64 • Chief complaint associated with pain from cold or hot • Chronic sensitivity associated with supragingival lesions • Pain not associated with decay • Fluent in English and able to read English at a 6th grade level • Pulpal response <40 via pulp tester • Active salivary flow from palpation of parotid and submandibular glands • Patients self reporting pain over 6/10 in the past week and/or the past 2 months
Exclusion Criteria

 • Pregnant women • Patients taking benzodiazepines, narcotics and multiple antidepressants for pain management not associated with the oral cavity • Unexplained xerostomia • Patients taking two or more medications associated with dry mouth • Pulpal response >40 via pulp tester • Patients requiring treatment for more than 5 decayed sites, periodontal disease and root canal therapy • Complicated medical history (>4 concurrent treatment for systemic diseases) • Lesion >1mm below the gumline

evaluation for salivary flow will be milking of the parotid gland and submandibular glands to evaluate flow. We will need to visualize the induction of salivary flow with physical stimulation for inclusion. Patient reported mouth dryness will be considered as an exclusion criteria. Pregnant women will also be excluded from the study. Participants suffering from chronic pain in other areas of the body and participants with prescription of narcotics to treat pain on a regular basis will be excluded because these characteristics may alter that data on pain associated from a V shaped lesion. Lesions that extend more than 1mm below the gumline will be excluded.

Study procedures

Participants will be recruited via flyers at the University of Michigan School of Dentistry and from emails of the flyer to the student providers operating in the dental undergraduate clinics. Participants will be initially screened in the undergraduate clinics by updating participants health history, completion of an exam, dental cleaning and by answering five questions from the Brief Pain Index about pain in the last 24 hours, week and month and right now. It is the standard of care the UMSoD for all patients to have a current exam and up to date cleaning. Exams and cleanings are not part of our study but must be up to date (within the past six months or year based on the recommendations of the American Dental Association and UMSoD protocol) in order for participants to take the 5 question pre-screen test modified from the Brief Pain Index. The 5 questions are: 1) Do you have any tooth pain? 2) Rate this pain at its worst over the past week. 3) Does this pain originate near the ditch in your tooth near the gum line? 4) Does this pain occur when you eat or drink something cold, like cold water or ice cream? 5) Can you point to the area that causes you the most pain? This pre-screen questionnaire will allow us to check participants prior to the enrollment process because of the large numbers of patients seen at the school and ensure that patient's dental oral health is being adequately addressed based on the guidelines of the UMSoD prior to enrollment in the study.

Once participants show interest in the study and meet the criteria in the pre-screening step, the participants will be then screened for inclusion and exclusion in the study with assessment of the Oral Health Impact Profile-49 (OHIP-49) and complete the pain assessment modified from brief pain inventory (BPI) to assess oral pain. The OHIP-49 questionnaire was selected due to its validation in oral health research in multiple population groups as well as evaluating the general oral health knowledge in participants[33]. Participants will also assess their level of pain on a specific tooth when pain is triggered with numerical pain scale based on questions relating to oral health modified from the BPI (See above for questions). This scale is highly validated in multiple age groups when assessing pain [34]. Because it is challenging to recapitulate tooth pain in a dental setting, we will use the scale based on triggers the participants experience in daily life from a modified BPI. Lastly, at every time point after the first appointment, we will include an additional survey- Patient's global impression of change (PGIC) scale. This measure has been highly validated in intervention studies and will add an extra evaluation of patient observed changed after the intervention.

Study Team

Study team personal that will conduct the initial screening for eligibility and complete the restoration will include the PIs, [name] and [name] and trained third year and fourth year dental students at the University of Michigan School of Dentistry. Blinded assessors will be different third and fourth year students that will be trained on how to implement the study. The dental students will be selected from students enrolled in the Health Advocacy arm of the Pathways program at the UMSoD, which is a graduation requirement. Typically students must show interest in a project prior to selecting a project. Research monies are also associated with each student of \$500 to support the research project. We anticipate 2-4 dental students to be involved in the PORT clinical study, but they have not been identified at this time.

Study Procedures

Once enrolled, the participants will be randomly assigned to control or treatment group. The control group participants will receive the gold standard treatment for V shaped lesions - a resin modified glass ionomer (Photac-fil®). Treatment group participants will receive their V shaped lesion restoration with Biodentine™. When they receive the restoration, all treatments will follow the standard of care for their placement and polishing at the UMSoD. Participants will be assigned a random number to identify them and will be blinded as to which treatment they will receive. Participants will fill out the same OHIP-49 and BPI questionnaire via a

survey link at 1 week, 2 weeks, and 3 months post treatment. If participants complete the survey, they will receive a monetary compensation of \$10 dollars/group of surveys completed for a potential of \$40 dollars to ensure participant compliance with the survey. Surveys will be completed at recall appointments on a secure survey system maintained by the UM medical school, REDCap and data will be stored on REDCap and backed-up to a secured University of Michigan Server. Expert assessors collecting patient information will be blinded as to the treatment the participant receives. At 3 months, the patients will receive a follow up evaluation of the filling, and an evaluation of the restoration placed at the V shaped lesion. Table 1 gives a visual breakdown of the study design. The restorative materials used in this study will be placed following manufacturer's instructions.

Table 2: Study Design

Timeline	Control Group (group size: 20) Study enrollment assigned random number	Treatment Group (group size: 20) Study enrollment assigned random number
Prescreen	Oral exam, dental prophylaxis, (Part of standard of care at UMSoD) pre-screen questionnaires modified from BPI	Oral exam, dental prophylaxis, (Part of standard of care at UMSoD) pre-screen questionnaire modified from BPI
Day 1 – Baseline	OHIP-49 BPI questionnaire	OHIP-49 BPI questionnaire
Day 1 - Baseline	Treatment: PHOTACFIL®	Treatment: BIODENTINE™
Week 1 - Follow-up (survey will be emailed and should be completed within 7 days)	OHIP-49 BPI questionnaire PGIC Scale	OHIP-49 BPI questionnaire PGIC Scale
Week 2 - Follow-up (survey will be emailed and should be completed within 7 days)	OHIP-49 BPI questionnaire PGIC Scale	OHIP-49 BPI questionnaire PGIC Scale
3 months (+/- three weeks)- Follow-up	OHIP-49 BPI questionnaire PGIC Scale Rationale: We expect an immediate elimination of pain but the impact on OHRQL will be more quantifiable if assessed over time.	OHIP-49 BPI questionnaire PGIC Scale Rationale: We expect an immediate elimination of pain but the impact on OHRQL will be more quantifiable if assessed over time.

Data Collection Procedures

Initially patients will be consented for enrollment and treatment in the study. Data for the clinical study will be collected multiple times during the study including prior to treatment, and 1 week, 2 weeks, and 3 months post treatment. Patients will receive an OHIP-49 questionnaire and a modified BPI and the third survey (PGIC scale) to relate to overall oral health via electronic emails. The surveys will be emailed to the participants via a secure survey source (REDCap) and completed electronically by the participants after their initial visit for the restoration placement. Patients will have 7 days to complete the email surveys and email reminders will be sent daily until the surveys are completed. If patients are unable to complete an emailed survey, they have the opportunity to return to the school to complete the surveys. The UMSoD has a supply of iPads® available for research purposes and will be used to collect data at the initial enrollment and if patients come to the school to fill out follow up surveys. There will be a 3-week window for subjects to return to the school for the 3-month follow-up visit.

Data management

All scanned data that goes to a digital form and acquired digital data will be kept on a secure server at the University of Michigan School of Dentistry that is password protected. A secure patient treatment record will be created with the patients assigned participant number, all paper materials returned from patients and participant consent materials will be kept in a locked cabinet in a locked office at the University of Michigan School of Dentistry..

Statistical Analysis Plan

Prior to testing primary study aims, we will examine data distribution characteristics to identify outliers and determine suitability of the data for parametric testing. Bivariate correlations will be conducted to identify important covariates for inclusion in main statistical models (e.g. age). Assuming underlying assumptions are met, we will use repeated measures of general linear models (GLM) to test for significant differences between the control and treatment groups in terms of changes in pain (specific aim 1) and oral health related quality of life (specific aim 2) over the course of the study. Significant group versus time effects will be examined graphically to determine the nature of the interaction and to qualify how pain and oral health related quality of life changed over time for each group.

Power Analyses

Currently, we do not have input data available to do an adequate sample size analysis or the study. For this small pilot study, we planned for a sample of 40 participants (20 subjects in control group and 20 in the experimental group) to generate some preliminary data for conducting a rigorous sample size analysis for a larger clinical trial

Potential Problems and Alternatives Strategies

In the event that we do not recruit enough patients to fulfill project timeline, we can recruit patients from the graduate clinic at the University of Michigan School of Dentistry and the emergency clinics.

In the event that either the control or treatment restoration falls off we will offer to replace the restoration and we will continue the measurement procedures. Due to the locations of the class V lesions, the stresses of the restoration during mastication may promote debonding of the restorations however, Biodentine has an increased risk of debonding. According to the manufacturer, Biodentine bonds well with dentin; however, no studies exist evaluating its bond strength in class V cervical lesions. If the Biodentine debonds, we will place a base layer of Biodentine to cover and seal the dentin and place Photac-fil® over top of that for added retention. This will allow Biodentine to remain in contact with the dentin but be more retentive. If a Biodentine restoration is placed in a shallow lesion that does not have a lot of natural retention, we will automatically place a Biodentine layer that is covered by Photac-fil®. Loss of restorative material will be covered under the grant for up to six months after initial placement of the restoration and will be noted in the patients record. If a participant has a restoration replaced, a new time line will be started for post-treatment evaluations just like a newly placed restoration. Additionally, Biodentine™ is not offered in multiple shades and patients may request that it is covered with a more esthetic restoration after the study is completed at the University of Michigan School of Dentistry (UMSoD).

Project feasibility

The undergraduate clinics have over 5,000 male and female patient visits per month for treatment of patients aged between 18-60. New patients are screened daily at the school and are continuously added to the patient population at the UMSoD. We plan to recruit from the dental undergraduate clinic. While we do not foresee enrollment issues, we can also access over 3,000 more patients in other clinics at the UMSoD by including the graduate clinics and faculty clinic. Given the high numbers of patients seen at the school of dentistry, we do not anticipate any difficulties in recruiting patients to meet enrollment numbers for the study.

Project Management and Project Timeline

The project principal investigator is [name] [name] and co-investigator is [name]. We will train and calibrate dental students to apply the materials as well as collect participant assessments as

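### Root canal treatment, extraction and pulp loss are not recorded after placement, so a tooth that is painless for one of these reasons could count as pain reduction

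*Combined protocol and SAP*

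**What the plan says.** **Entry.** The Participants section states "The affected teeth will have the pulp vitality evaluated with an electronic pulp tester" and "Pulp test readings must be below 40 to be considered for the study". The same section and Table 1 exclude people who need root canal treatment. Baseline pain "must register over a 6 point in the self-report brief pain inventory index for each question asked to the patient", and on the scale the section says "Both of these short assessments will be measured on a 1-10 Likert scale".

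**Follow-up.** Study Procedures, Table 2, Data Collection Procedures and section 1.3 of Protection of Human Subjects list the same instruments: OHIP-49, a modified BPI and the PGIC scale, at 1 week, 2 weeks and 3 months. The 3-month visit adds a check of the filling and "an evaluation of the restoration placed at the V shaped lesion". No pulp reading is named there. The pulp tester appears once more, in section 1.4.1.1, only as a source of minor discomfort.

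**Events after placement.** Potential Problems and Alternatives Strategies has a rule for a lost restoration. No section covers root canal treatment, extraction or pulp disease of the restored tooth, and none sets out adverse event collection.

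**Analysis.** The Statistical Analysis Plan says "we will use repeated measures of general linear models (GLM) to test for significant differences between the control and treatment groups" on change in pain and in quality of life. It defines no responder or success criterion and does not say how scores are used after an intervening event.

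**Rationale.** Specific Aims and Innovation argue through the pulp. The control material may inflame it, materials in these lesions can "cause more irritation in the pulp and perceived pain", and Biodentine may reduce that response.

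**The concern.** The pain outcome depends on a living pulp. Specific Aims attributes the pain to nociceptors in the pulp, and Study Procedures bases the ratings on triggers met in daily life. A low score at 3 months can therefore mean two different things: the exposed dentin is sealed and the pulp is settled, or the pulp no longer responds because it has been lost, removed or extracted with the tooth. The planned data cannot separate them.

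With no rule in the plan, scores enter the model as reported. A participant in the second situation then adds to the arm's apparent pain reduction, and the event appears nowhere as a harm. Power Analyses says the trial is meant to supply inputs for a larger one. That trial would inherit pain data that may include such scores, and no count of the events. The information is hard to recover later if nobody asks at the visit.

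**Working it through.** The plan has no figure to reproduce: Power Analyses says that no inputs were available and sets 20 per arm as a pilot number. The steps below only give the scale.

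**Inputs from the documents:** 20 per arm; a scale from 1 to 10, so a floor of 1; entry pain above 6, taken as 7 to 10 in whole points.

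**Assumptions, not in the documents:** the event rate, an SD of 2 to 3 points, and two-sided alpha 0.05.

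1. *Worst-case shift from one event.* Suppose the participant scores 1 instead of staying at baseline. The arm mean moves by (baseline − 1)/20.
   - Baseline 7: (7 − 1)/20 = 0.30 points.
   - Baseline 10: (10 − 1)/20 = 0.45 points.
   - Two events in one arm double this to 0.60 and 0.90.

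2. *Shift if pain would have fallen anyway.* The 3-month row of Table 2 expects pain to be eliminated at once. Had the participant otherwise scored 3, the shift is (3 − 1)/20 = 0.10. Had the score been 1, it is zero.

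3. *In SD units, baseline 7.* One event: 0.30/3 = 0.10 to 0.30/2 = 0.15. Two events: 0.20 to 0.30. For comparison, 20 per arm gives 80% power for a standardised difference of 0.886.

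4. *Effect on a test with no true difference.* Use a normal approximation at one time point, with SE = SD × √(2/20), and probability 1 − Φ(1.96 − shift/SE) of a significant result favouring the affected arm. Without any shift this is 2.5%.
   - One event (shift 0.30): 5.0% at SD 3, 6.9% at SD 2.
   - Two events (shift 0.60): 9.2% at SD 3, 15.6% at SD 2.
   - These use the worst-case shift from step 1. They do not evaluate the full repeated-measures model.

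5. *Chance of at least one event in an arm of 20,* 1 − (1 − p)^20, for assumed per-participant rates p:

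| p | Chance |
|---|---|
| 1% | 18% |
| 2% | 33% |
| 5% | 64% |
| 10% | 88% |

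6. *Value of a recorded zero.* With 0 of 20, the one-sided 95% upper bound is 1 − 0.05^(1/20) = 13.9%. With 0 of 40 it is 1 − 0.05^(1/40) = 7.2%. Without recording, not even this bound can be stated.

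**The case against.** A reader might infer that the very harm behind the hypothesis is scored as benefit. The documents do not support that. Specific Aims and Innovation link pulp irritation to more pain, so a failing pulp may first show as worse scores at 1 or 2 weeks. Only a tooth that is painless on a survey date is affected. A reader might also say that harm becomes a treatment success, but the plan defines no success and the effect is on mean change.

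The size is also open to challenge. Events in three months may be few or none: lesions are non-carious, a need for root canal treatment excludes, and section 1.4 says the restorations involve no tooth preparation. Up to two sites may be filled per participant, so one pulpless tooth need not bring a shared score to the floor. Only time points after the event are touched. All of this stands, and it makes 0.30 to 0.45 a ceiling.

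Finally, analysing scores as reported is a legitimate choice, and carrying the baseline forward is single imputation that would also count an extraction for an unrelated reason against the material. That stands as well, so the unfavourable rule belongs in a sensitivity analysis.

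What the objection does not answer is the gap itself. Nothing in the documents records these events or says how later scores are used.

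**Conclusion.** The gap is real, and its effect on the result is limited and uncertain. Pulp status and root canal need are checked at entry only. A tooth that is painless because of pulp loss, root canal treatment or extraction could enter the Specific Aim 1 model as pain reduction. The shift favours whichever arm has more such teeth, and the documents give no basis for saying which arm that is.

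The worst case is 0.30 to 0.45 points on a 20-person arm mean per event at the affected time points. This assumes a baseline of 7 to 10, a fall to 1, and no improvement otherwise. It is smaller, possibly zero, if pain would have fallen anyway or if a second filled site keeps the score up. The event rate is not given and may be zero. The change is still worth making because the data are cheap to collect at a visit that already exists, and because the pulp is central to the trial's own rationale.

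**What to change.** - **Record.** At the existing 3-month visit, record by enrollment number, for each restored tooth, any root canal treatment, extraction, diagnosed pulp disease or other treatment for pain, with its date. Ask the participant directly, so that treatment elsewhere is captured. Section 2.2.2 already links records through the enrollment number.
- **Report.** List these events by arm as harms.
- **Analyse.** State that the main Specific Aim 1 analysis uses scores as reported. Prespecify one sensitivity analysis in which scores after a root canal, extraction or pulp loss on the restored tooth are treated as unfavourable, for example set to the participant's baseline. Other pain treatment is listed only.
- **State the limitation.** Without a repeat pulp test, silent pulp loss may still be missed.

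The cost is a few form fields and one additional analysis. No new visit or procedure is needed, and how such teeth are managed clinically is left untouched.
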